Data collection: After successful screening, women will be asked to take 14 days of EFV in a once-nightly 400 mg regimen. We will collect blood samples for baseline ENG concentration on the day participants begin taking EFV, before the first dose (Day 1, times 0 hour, 1 hour, and 2 hours). The first dose of EFV will be taken in the evening of Day 1, and the next blood sample for ENG concentration will be drawn twelve to twenty hours after the first dose of EFV. (For example, if a participant takes her first dose of EFV at 10 PM on Day 1, she will be asked to return to the CRU between 10 AM and 6 PM on Day 2.) We will then obtain subsequent samples every 3 to 4 days (+/- 1 day) for the remainder of the two week EFV course and for 4 additional weeks (through Week 6 of study participation). This is a total of 14 outpatient visits, including screening. All serum samples will be analyzed for concentrations of ENG, which will be used to derive the ENG area under the concentration-time curve (AUC), the maximum and minimum observed serum drug concentration (C_{max}, C_{min}), and the apparent average serum concentration at steady-state (C_{ss,avg}) using WinNonlin®. EFV concentrations will be determined from plasma samples obtained at 2 timepoints during EFV administration, and measured using a validated LC/MS/MS assay in the Clinical Pharmacology Analytical Laboratory of the Johns Hopkins Hospital.

Table 1: Participant Visit Schedule and Timing of Study Assessments

Visit	Screening	Study Entry			Week 1		Week 2		Week 3		Week 4		Week 5		Week 6	
		1			2	7	11	14	18	21	25	28	32	35	39	42
Serum Tests		0 hr	1 hr	2 hr												
ENG		X	X	X	X	X	X	X	X	X	X	X	X	X	X	X
EFV					X			X								
FSH		X			X	X	X	X	X	X	X	X	X	X	X	X
LH		X			X	X	X	X	X	X	X	X	X	X	X	X
Estradiol		X			X	X	X	X	X	X	X	X	X	X	X	X
Progesterone		X			X	X	X	X	X	X	X	X	X	X	X	X
Safety Labs	X															X
UPT	X															X
HIV	X															X
TVUS	X				X	X	X	X	X	X	X	X	X	X	X	X
CM	X				X	X	X	X	X	X	X	X	X	X	X	X

Date: January 5th, 2017

Principal Investigator: [name], MPH

Application Number: NA_00087585

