- Nervous system symptoms: dizziness, insomnia, impaired concentration, somnolence, abnormal dreaming, euphoria, confusion, agitation, amnesia, hallucinations, stupor, abnormal thinking, depersonalization. Mild symptoms occurred in 33.3% of patients taking EFV compared to 15.6% of patients in control groups; moderate symptoms occurred in 17.4% of patients taking EFV compared to 7.7% of controls; and severe symptoms occurred in 2% of patients taking EFV compared to 1.3% of controls.
- Rash: 26% of patients taking EFV developed a rash compared to 17% of patients in control groups. A grade 4 rash (erythema multiforme, Stevens-Johnson syndrome, toxic epidermal necrolysis, necrosis requiring surgery, exfoliative dermatitis) was seen in 0.1% of patients treated with EFV and no patients in control groups. Rashes usually occur during the first two weeks of treatment, and are mild-to-moderate maculopapular skin eruptions. The rash typically resolves within one month in patients who continue EFV.
- Hepatotoxicity: it is recommended that liver enzymes be evaluated before and during treatment with EFV, as EFV can cause elevated liver enzymes even in patients without underlying hepatic disease.
- Convulsions: Convulsions have been noted in patients treated with EFV, typically in the setting of a known seizure disorder.
- Lipid elevations: EFV can lead to increased concentrations of total cholesterol and triglycerides. Some HIV-uninfected volunteers who received EFV were noted to have 10-20% increases in total cholesterol from baseline.

Date: January 5th, 2017

Principal Investigator: [name], MPH

Application Number: NA_00087585

- **Fat redistribution:** Body fat may redistribute or accumulate in certain regions of the body, including central obesity, dorsocervical fat enlargement (buffalo hump), peripheral wasting, facial wasting, breast enlargement, and “cushingoid appearance.” This phenomenon has been noted among patients taking antiretroviral therapy in general, and while it has not been specifically linked to EFV, it is a potential adverse reaction to this drug.
- c. Justification and safety information if non-FDA approved drugs without an IND will be administered.

Not applicable

7. Study Statistics

- a. Primary outcome variable.

Primary Outcome: Serum concentrations of ENG before and after two weeks of reduced-dose EFV

- b. Secondary outcome variables.

Secondary Outcomes:

- Serum concentrations of EFV at the start and end of the study period

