- Serum hormonal markers of ovulation (P, E₂, LH, FSH)
- Presence of dominant follicle(s) on transvaginal ultrasound during and after EFV dosing
- Change in cervical mucus quality suggesting ovulation during and after EFV dosing

- c. Statistical plan including sample size justification and interim data analysis.

Sample size: We hypothesize that during co-administration of the ENG implant and reduced-dose EFV, we will detect a decrease in serum ENG concentrations, but that overall contraceptive effect will be maintained. We do not anticipate that any subjects will have a drop in ENG concentration below the threshold needed for ovulation suppression (90 pg/mL)[8]. Using a two-sided Wilcoxon test, a sample size of 15 will have 80% power (with an alpha of 0.05) to detect a 20% difference in ENG concentration between women taking EFV and historical controls. We plan to enroll 18 women to account for a potential 20% drop-out rate.

Data Analysis: We will calculate area under the curve (AUC) and maximum and minimum concentrations of each drug (C_{max} and C_{min}), as noted above. For hormone markers (LH, FSH, E₂, P) we will evaluate change over time as well as whether pertinent threshold levels are reached that could indicate that ovulation has occurred. All serum tests will be evaluated through the Johns Hopkins Division of Clinical Pharmacology, with the exception of etonogestrel concentrations as this assay is not widely available. Serum samples will be frozen and shipped to the Irving Institute for Clinical and Translational Research at Columbia University Medical Center in New York City, which will perform the etonogestrel assay.

Interpretation: If the pharmacokinetic parameters for etonogestrel that are seen in this interaction study are consistent with those published in the literature (less than 30% difference), we will conclude that there is no significant interaction between ENG and reduced-dose EFV. This would support the assertion that Nexplanon®/Implanon® is a safe and effective option for HIV-infected women taking reduced-dose EFV who desire long-acting reversible contraception. However, if two or more women out of a sample of 15 breach the threshold concentration needed for ovulation suppression, it will indicate a statistically and clinically significant decrease in ENG concentration and potential for decreased contraceptive efficacy.

Date: January 5th, 2017

Principal Investigator: [name], MPH

Application Number: NA_00087585

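### The 30% rule clears an interaction on the observed difference alone, with no confidence limit and no deciding parameter, so an observed fall of roughly 20-30% passes without excluding a fall beyond 30%

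*Combined protocol and SAP*

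**What the plan says.** Section 7c (Interpretation) holds two decision rules.

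- **Clearance.** If the observed ENG parameters "are consistent with those published in the literature (less than 30% difference), we will conclude that there is no significant interaction". This is said to support the assertion that the implant "is a safe and effective option for HIV-infected women taking reduced-dose EFV who desire long-acting reversible contraception".
- **Breach.** "However, if two or more women out of a sample of 15 breach the threshold concentration needed for ovulation suppression", the plan reads this as a decrease that is significant both statistically and clinically. The threshold is 90 pg/mL.

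The only inferential element is a Wilcoxon test (two-sided). The sample-size paragraph claims for it that "a sample size of 15 will have 80% power (with an alpha of 0.05) to detect a 20% difference in ENG concentration", against historical controls. The hypothesis is that "we will detect a decrease in serum ENG concentrations, but that overall contraceptive effect will be maintained", and the plan adds: "We do not anticipate that any subjects will have a drop in ENG concentration below the threshold needed for ovulation suppression".

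Section 4a lists AUC, Cmax, Cmin and Css,avg as the ENG parameters to be derived, and none is ranked. The primary outcome in Section 7a is "Serum concentrations of ENG before and after two weeks of reduced-dose EFV".

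**The concern.** An observed difference below a margin does not show that the true difference is below it. That needs an interval or an equivalence test, and the document specifies neither. The Wilcoxon test does not fill the gap, because it asks whether there is any difference and not whether a fall is smaller than 30%.

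The rule also speaks of parameters in the plural. It does not say which of the four decides, or what follows if some are within 30% and others are not.

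The conclusion at stake is a definite negative one. It would be offered in support of contraceptive safety, and Section 9a expects the data to guide later studies. The plan has no category for data that leave the question open.

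**Working it through.** **Inputs from the plan:** n = 15 evaluable; margin 30% (ratio 0.70); two-sided Wilcoxon test, alpha 0.05, 80% power for a 20% difference; breach threshold 90 pg/mL, 2 or more of 15 women.

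**Inputs not in the plan:** the SD, baseline ENG, and the size of the literature sample. All are assumed or back-solved below.

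**1. The plan's own figure.** n = 15 cannot be reproduced without an SD, so I solved for the SD that yields it. On the log scale a 20% fall is ln 0.80 = -0.223.

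- One-sample or paired signed-rank test: log-SD 0.28 gives 79.5% power in an exact-test simulation.
- Rank-sum test, 15 versus 15: 80% power needs a log-SD of about 0.20. At 0.28 the power is only about one half.

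The plan does not say which Wilcoxon test is meant. I therefore use 0.20 and 0.28, and add 0.40 as an assumed high value.

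**2. What an observed 25% fall leaves open.** One parameter, literature mean taken as known. The 90% half-width is t(0.95; 14) × SD/√15, with t = 1.761. The far end of the interval is a fall of 1 - 0.75 × exp(-half-width).

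| Log-SD | SD/√15 | Half-width | 90% CI reaches a fall of |
|---|---|---|---|
| 0.20 | 0.0516 | 0.091 | 31.5% |
| 0.28 | 0.0723 | 0.127 | 34.0% |
| 0.40 | 0.1033 | 0.182 | 37.5% |

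On the two-sample reading (log-SD about 0.205, standard error 0.205 × √(2/15) = 0.0749, t = 1.701 on 28 df) the interval also reaches about 34%.

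**3. How often the rule clears a true fall beyond the margin.** The probability is Φ[(ln r - ln 0.70)/(SD/√15)] for true ratio r, before the breach rule.

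| True fall | SD 0.20 | SD 0.28 | SD 0.40 |
|---|---|---|---|
| 35% (r = 0.65) | 7.6% | 15.3% | 23.7% |
| 40% (r = 0.60) | 0.1% | 1.6% | 6.8% |

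**4. With the breach rule overriding.** I simulated one log-normal on-EFV value per woman (log-SD 0.28), with the literature value equal to the assumed baseline median. A true 35% fall is then cleared as follows.

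| Baseline median (pg/mL) | 150 | 175 | 200 | 250 |
|---|---|---|---|---|
| Cleared | 1% | 8% | 14% | 15% |

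The pattern follows from the absolute threshold: after a 35% fall, a woman who starts above 90/0.65 = 138 pg/mL stays above 90. Counting breaches at every visit would lower these figures.

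The plan expects no breaches, which fits the higher medians better. At a 20% fall the expected number of breaching women is 15 × Φ[ln(90/(0.8 × median))/0.28] = 2.3, 0.9, 0.3 and 0.03.

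**5. With a confidence limit added.** The lower 90% limit exceeds 0.70 only if the observed fall is below 1 - 0.70 × exp(half-width). Pass rates come from the noncentral t distribution.

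| | SD 0.20 | SD 0.28 | SD 0.40 |
|---|---|---|---|
| Largest observed fall that passes | 23.3% | 20.5% | 16.0% |
| Pass rate, true 35% fall | 0.1% | 0.4% | 1.0% |
| Pass rate, true 20% fall | 79% | 54% | 34% |
| Pass rate, true 15% fall | 97% | 82% | 56% |

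**The case against.** Several parts of the defence stand.

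- **The breach rule already overrides.** The breach sentence opens with a contrast, and its conclusion cannot coexist with no significant interaction. A reader might infer that the two rules conflict; the natural reading is that the breach rule wins. Step 4 shows that it protects well when baseline ENG is low and little when it is high.
- **Large falls are rarely cleared.** A reader might infer that the rule would pass a gross interaction. Step 3 does not support that.
- **A coin-toss at the margin is not special to this plan.** A true fall of exactly 30% is cleared half the time, but so it is under any one-parameter point-estimate rule at its own margin. If all parameters must pass, the figure is lower still.
- **The 20% and 30% figures do not contradict each other.** A detected fall below 30% is what the plan hypothesises. A relevance margin above the detectable effect is legitimate, and here the word significant evidently means clinically relevant.
- **This is a pilot.** The result would support an assertion rather than settle it, and ovulation hormones, ultrasound and cervical mucus are also collected.

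The pilot status does not answer the central point, because the rule still issues a definite negative conclusion. The pharmacodynamic data do not answer it either, because the 30% rule makes no reference to them.

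**Conclusion.** The concern holds in a limited form. The stated rule clears observed falls of roughly 20-30% on data that do not exclude a fall beyond the plan's own margin, and it leaves the deciding parameter open.

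The direction needs no assumed variance; the size does. The SD of 0.28 follows from the power statement only for a one-sample or paired signed-rank test, 0.20 follows from a rank-sum test, and 0.40 is assumed. The baseline medians are also assumed. Treating the literature mean as known favours the plan, since its uncertainty would widen every interval.

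The documents do not support reading this as a plan that would miss a large interaction, or as one with contradictory rules. The concentration data remain valid whichever rule is used. It should be fixed, because the conclusion concerns contraceptive protection and the repair is a few sentences.

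**What to change.** **Core change, in Section 7c (Interpretation):**

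- Name the ENG parameter that decides, or state that all must pass.
- Report its geometric mean ratio with a 90% confidence interval.
- Conclude no clinically relevant interaction only if the lower limit exceeds 0.70 and the breach rule is not met. If the breach rule is met, report the plan's breach conclusion. Otherwise report that an interaction is not excluded.
- If the literature comparison is kept, include the uncertainty of the literature mean in the interval.

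**Separate, optional change of comparator.** The plan sets its 30% margin against published values. A within-woman ratio of on-EFV to pre-dose ENG could replace that comparison, but the plan should say so openly and restate the margin for it. This would match the before/after primary outcome and use samples already scheduled: "We will collect blood samples for baseline ENG concentration on the day participants begin taking EFV, before the first dose", with ENG sampled again on Day 14. A rule for combining the three Day 1 samples is needed.

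**Cost.** No new visits or samples are needed, but the claim is harder to earn. With the comparator held fixed, the observed fall must be under about 23%, 20% or 16% at log-SD 0.20, 0.28 or 0.40, and a true 20% fall passes in about 79%, 54% or 34% of trials. If the literature mean comes from an assumed 20 women with the same SD, those pass rates drop to about 61%, 39% and 25%. A trial that fails the rule reports an open question, which is what such data show.

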TITLE: Pharmacokinetics and pharmacodynamics of the etonogestrel contraceptive implant when co-administered with efavirenz

NCT: NCT01980342

DATE: January 5th 2017

PI: [name], MPH

JHM IRB - eForm A – Protocol

1. Abstract

Women of reproductive age who are living with HIV have to navigate complex decisions regarding fertility, contraception, and managing their HIV diagnosis. One consideration for HIV-infected women who want or need to prevent pregnancy is whether the medications used to treat HIV could reduce the efficacy of a contraceptive method through drug-drug interactions. Efavirenz (EFV) is a non-nucleoside reverse transcriptase inhibitor (NNRTI) that is an important component of first-line antiretroviral therapy worldwide. However, in addition to having a side effect profile that leads some to discontinue therapy, Efv has been associated with failures of a highly effective hormonal contraceptive, the etonogestrel (ENG) implant. A recent multi-center trial suggests that a lower Efv dose retains efficacy against HIV while reducing the incidence of side effects. We propose a pilot study to evaluate the effect of reduced dose Efv on the pharmacokinetics of the ENG implant. We will recruit 18 HIV-negative healthy women who have had the implant in place for 6 to 30 months. They will be asked to take a two-week course of reduced dose efavirenz. During these two weeks and for four additional weeks, we will monitor semi-weekly ENG concentrations, and serum, ultrasound, and cervical mucus markers of ovulation. We will also assess Efv concentration at baseline, the end of the two-week treatment course, and at the end of the study. We will derive pharmacokinetic parameters and compare concentrations across time points. Results will help determine whether the ENG implant can be used safely by HIV-positive women taking Efv, and will help to inform the design of similar larger studies with different antiretroviral medications.

2. Objectives

The primary objective of this study is to determine whether etonogestrel (ENG) pharmacokinetics in users of the ENG contraceptive implant (Nexplanon®/Implanon®) are affected by concomitant administration of a reduced dose of oral efavirenz (EFV).

Secondary objectives are:

- To determine if co-administration of reduced-dose efavirenz with the ENG contraceptive implant results in pharmacodynamic changes that suggest increased risk of ovulation and consequently decreased contraceptive efficacy.

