This will be a prospective, single arm pilot pharmacokinetic (PK) study. We will recruit 18 healthy, HIV-negative women aged 18 to 40 years who are using Nexplanon®/Implanon® for contraception and who are willing to take a reduced dose of EFV for 2 weeks. We will limit enrollment to women who have had the ENG implant in place 12 to 24 months to avoid the initial burst release of ENG after implant placement, and to target the time frame of concern based on case studies of contraceptive failures among women on HAART. Performing the study in women without HIV infection will allow us to evaluate any interactions between ENG and EFV without having to contend with the effects of other drugs that make up typical HAART regimens. A two-week course of EFV will be sufficient for EFV to reach steady-state concentration while minimizing exposure in these healthy volunteers. By using the reduced dose of EFV (400 mg daily instead of the standard 600 mg daily dose)

Over 6 weeks from study entry, we will perform twice-weekly (see visit schedule) quantitative assessments of serum ENG as well as serum hormone concentration analysis, pelvic ultrasound for markers of ovulation, and cervical mucus testing, as described below. Given the slow apparent clearance of ENG and based on previous PK studies, we estimate that sparse sampling will be adequate to assess changes in ENG clearance during EFV administration. EFV will be administered for 14 days from the beginning of the study, after collection of baseline samples for ENG concentration determination. All study procedures will take place at the Johns Hopkins Bayview Medical Center's Clinical Research Unit (CRU). All blood tests will be performed locally except for ENG concentrations, which will be performed at Columbia University

Date: January 5th, 2017

Principal Investigator: [name], MPH

Application Number: NA_00087585

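### The 30% no-interaction rule judges ENG against unnamed published values rather than each woman's own baseline, so it cannot separate an EFV effect from a cohort difference

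*Combined protocol and SAP*

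**What the plan says.** Section 7a defines a before/after outcome: "Primary Outcome: Serum concentrations of ENG before and after two weeks of reduced-dose EFV". The Abstract points the same way: "We will derive pharmacokinetic parameters and compare concentrations across time points". Section 4a (Data collection, Table 1) provides the data for it: three ENG samples on Day 1 before the first EFV dose, ENG samples on Days 2, 7, 11 and 14, and then samples to Day 42.

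The Interpretation paragraph of 7c, which holds the only rule for concluding that there is no interaction, uses a different comparison. If the ENG parameters are "consistent with those published in the literature (less than 30% difference), we will conclude that there is no significant interaction". The sample-size sentence in 7c also looks outside the study: the test is meant "to detect a 20% difference in ENG concentration between women taking EFV and historical controls".

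The parameters are listed in two places. Section 4a says "All serum samples will be analyzed for concentrations of ENG, which will be used to derive the ENG area under the concentration-time curve (AUC", and adds Cmax, Cmin and Css,avg. In 7c (Data Analysis): "We will calculate area under the curve (AUC) and maximum and minimum concentrations of each drug". Neither place says over which days these are computed when the 30% rule is applied.

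**The concern.** A comparison with published values measures two things at once: what EFV did to these women, and how these women differed from the published ones before any EFV. Section 9a (Benefits) itself says that ENG falls slowly over the three years of the implant, so a published value depends on implant age. The plan names neither a value nor an age.

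The rule matters because 7c says that a pass would support the implant as a safe and effective option for HIV-infected women on reduced-dose EFV. If this cohort starts above the published level, a real fall of more than 30% can pass. If it starts below, a small fall, or none, can be flagged. The Day 1 samples that would remove this ambiguity are already scheduled, but no decision in 7c uses them.

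**Working it through.** **1. The plan's own figure.** Section 7c states 15 women, 80% power, two-sided alpha 0.05 and a 20% difference by a Wilcoxon test. It gives no SD and does not say whether the test is signed-rank or rank-sum, so the figure cannot be reproduced. It can only be inverted.
- One sample or paired: standardised effect = (1.96 + 0.84)/√15 = 0.723, so SD = 20%/0.723 = 27.6% of the reference. With the Wilcoxon efficiency of 3/π it is 27.0%; simulation gives about 25%.
- Rank-sum with 15 per group: about 19 to 20% by formula, about 18% by simulation.

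Neither SD is stated in the plan.

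**2. Comparator.** Let f be the true within-woman fall at Day 14 and k the cohort baseline divided by the published value. The documents give neither. The calculation ignores sampling noise.
- Observed ratio to the published value = k(1 − f).
- The value is less than 30% below the published one while k(1 − f) > 0.70.
- Switch point: f = 1 − 0.70/k.

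| k (assumed) | True fall at which the rule switches |
|---|---|
| 0.70 | 0% (flags with no EFV effect) |
| 0.8 | 1 − 0.875 = 12.5% |
| 0.9 | 1 − 0.778 = 22% |
| 1.0 | 1 − 0.700 = 30% |
| 1.1 | 1 − 0.636 = 36% |
| 1.2 | 1 − 0.583 = 42% |

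Two cases: at k = 1.2 a true 40% fall reads as 1.2 × 0.60 = 0.72, a 28% difference, and passes. At k = 0.8 a true 20% fall reads as 0.8 × 0.80 = 0.64, a 36% difference, and is flagged.

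**3. Own baseline.** The within-woman ratio is (1 − f), because each woman's starting level cancels. It switches at f = 30% for every k.

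**4. Window (secondary).** AUC grows with the length of the interval. A flat concentration C gives 13C over Days 1–14 and 41C over Days 1–42, a factor of 41/13 = 3.2 with no change in exposure. A percentage difference from a published AUC has no meaning until the interval is fixed.

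Restricting to on-EFV samples does not settle it, because "the next blood sample for ENG concentration will be drawn twelve to twenty hours after the first dose of EFV". That Day 2 sample may still be near baseline. As an illustration, take a 50% fall at Day 14 and assumed onsets (half-life 2 to 5 days, or linear over 7 or 12 days). The Day 2 value is then down only 2 to 13%, so an on-EFV Cmax stays close to the pre-EFV level.

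**5. Power for the paired form.** The mean log ratio for a 20% fall is ln 0.80 = −0.223. For 15 women, a simulated two-sided signed-rank test at alpha 0.05 (20,000 runs per SD) gives power of 0.91 at a log-ratio SD of 0.24, 0.80 at 0.28 and 0.74 at 0.30. All three SDs are assumptions.

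**The case against.** Several points on the other side are fair.

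- **The historical comparison is a declared choice.** The power sentence and the 30% rule agree with each other. That stands, but neither agrees with 7a, and no published value is named.
- **Enrolment limits the cohort difference.** Sections 4a and 5 restrict implant use to 12–24 months and BMI to below 30. This narrows the likely range of k, but does not fix it, because the age and weight of the published women are not stated. The Abstract gives 6 to 30 months, which must be reconciled with sections 4a and 5.
- **This is a pilot with a second criterion.** The count of women below 90 pg/mL is a separate, individual-level rule. It neither defines nor corrects the 30% rule.

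Three stronger readings are tempting, and the documents do not support them.

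- A reader might infer that the rule names no parameter, so the verdict could be picked from whichever one passes. The parameters are listed in 4a and 7c, and the plural in the rule most naturally means all of them.
- A reader might infer that AUC and Cmax would be pooled over Days 1–42, so that washout and baseline samples hide a fall. No passage says so. Section 4a says "sparse sampling will be adequate to assess changes in ENG clearance during EFV administration", 7a is time-specific, and the follow-up after EFV is given its own purpose of watching contraceptive effect.
- A reader might try to bound the falls that could pass by requiring every parameter to lie within 30%. That needs the same k for each parameter, and nothing supports it: section 9a places the peak a mean of 4 days after insertion, so a published Cmax may belong to a different phase of implant use.

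**Conclusion.** The concern holds for the comparator. The decision rule in 7c is not tied to the before/after outcome in 7a. With k between 0.8 and 1.2, the true fall at which its verdict changes runs from 12.5% to 42%. The formula needs no assumption about onset or recovery rates. It rests on applying the rule to the Day 14 value, on ignoring noise, and on a range for k that is my assumption. The documents do not show which way k departs from 1, so they do not support saying that the rule is biased towards finding no interaction.

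The missing window is a real but secondary gap; alone it would be a matter of missing detail. The scheduled data are sound, so this should be corrected in the analysis text and does not undermine the design.

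**What to change.** In 7c:

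- Apply the 30% rule to the within-woman ratio of Day 14 ENG to baseline, with baseline as the mean of the three Day 1 pre-dose samples. Summarise it as a geometric mean ratio with its confidence interval, and state whether the point estimate or an interval limit must clear 30%. At an assumed log-ratio SD of 0.28, a point estimate from 15 women would still pass about 15% of the time at a true 35% fall.
- If Day 14 is missing, use the last available on-EFV sample, with the Day 11/14 mean as a sensitivity analysis. Section 4f allows up to three missed visits, so that sample could be Day 2; report how often this occurs.
- Report AUC as time-averaged concentration within the on-EFV window, and recovery (Days 18–42) separately.
- Keep the literature comparison as descriptive, with the published values and implant ages named. Keep the 90 pg/mL count as a separate criterion.
- Restate the power sentence for the paired test with its assumed SD: 15 women give about 80% power for a 20% fall if the SD of the log ratio is about 0.28.

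Cost: wording only, with no change to samples or assays. The literature comparison ceases to be the formal basis for the verdict, and the power sentence must be rewritten around an SD that the plan does not now state.

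### The two interpretation rules in Section 7c overlap and leave a gap, and the breach rule has neither a test nor a baseline condition

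*Combined protocol and SAP*

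**What the plan says.** The Interpretation paragraph of Section 7c gives two rules.

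- **Rule 1, a group comparison with published values.** It applies when the ENG results prove "consistent with those published in the literature (less than 30% difference), we will conclude that there is no significant interaction". The plan adds that such a result favours the implant as safe and effective for HIV-infected women on reduced-dose EFV.
- **Rule 2, a count of women.** Introduced by *However*, it is triggered when at least two of the 15 fall under the threshold. The stated reading is then that "it will indicate a statistically and clinically significant decrease in ENG concentration and potential for decreased contraceptive efficacy".

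The sample-size paragraph of the same section identifies the "threshold needed for ovulation suppression (90 pg/mL"). It hypothesises that ENG will fall while contraceptive effect is maintained, and expects no woman to drop below the threshold. The only test named there ("Using a two-sided Wilcoxon test") is for a 20% difference in concentration from historical controls. Section 7a defines the primary outcome as ENG before and after two weeks of EFV.

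**The concern.** One rule is a group difference and the other is a count, so each can be met or not met independently of the other. That makes four outcomes, and the plan speaks clearly to only two of them. Where both rules are met, the text offers a conclusion of no interaction and a conclusion of significant decrease from the same data. Where neither is met, it offers nothing.

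Rule 2 has two further weaknesses. It claims statistical significance with no test, null rate or error level attached to the count. It also speaks of a decrease without looking at where each woman started: the inclusion criteria in Section 5 set no minimum ENG concentration, so a woman already below 90 pg/mL before her first EFV dose is not excluded from the count.

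The conclusion is meant to inform whether women on EFV can rely on this implant. If the reading of an awkward result is not fixed in advance, it will be settled after the data are seen.

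**Working it through.** **Inputs from the plan (Section 7c):** 30% margin; 90 pg/mL threshold; two or more breaches; 15 women. The plan gives no baseline mean, SD or CV, and no null rate for breaches.

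**Step 1. The four outcomes.**

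| Difference | Breaches | What Section 7c concludes |
|---|---|---|
| under 30% | 0–1 | no significant interaction |
| under 30% | 2 or more | both rules met, wording opposed |
| 30% or more | 2 or more | significant decrease |
| 30% or more | 0–1 | nothing stated |

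**Step 2. Are the second and fourth rows reachable?** The starting value from which a 30% fall lands exactly on the threshold is 90/0.70 = 128.6 pg/mL. A woman starting below that can breach after a fall of less than 30%. A woman starting above it can fall 30% and not breach. So both rows are reachable.

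Examples, with an *assumed* published mean of 200 pg/mL:

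- Two women at 86 and 88 and thirteen at 160: (86 + 88 + 13 × 160)/15 = 2254/15 = 150.3, and 1 − 150.3/200 = 24.9%. Both rules are met.
- Fifteen women at 120: 1 − 120/200 = 40%, with no breach. Neither rule is met.

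The second example is a decrease with no woman below the threshold, which is what the plan hypothesises.

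**Step 3. Is two of 15 statistically significant?** With background breach rate p, P(2 or more of 15) = 1 − (1 − p)^15 − 15p(1 − p)^14.

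- p = 2.42%: 1 − 0.692 − 0.258 = 0.050
- p = 5%: 1 − 0.463 − 0.366 = 0.171
- p = 10%: 1 − 0.206 − 0.343 = 0.451

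The rule holds a 5% level only if about 2.4% of women or fewer would be below 90 pg/mL without EFV. If all 18 enrolled women were evaluable, the probability would already be 0.0495 at p = 2%. The exact (Clopper–Pearson) 95% interval for 2/15 runs from 1.7% to 40.5%.

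**Step 4. How often would the problem rows occur?** This needs assumptions that the plan does not supply: lognormal ENG, published mean equal to the true baseline mean, between-woman CV 30–40%, within-woman log-SD 0.12, n = 15, breaches counted on Day 14. Rule 1 is applied as written, against the published mean.

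- True fall 20%, both rules met: 74–80% of trials at a baseline mean of 150 pg/mL, 31–53% at 175, 7–25% at 200, 0.2–3% at 250.
- True fall 35%, neither rule met: 9–29% at 200, 49–74% at 250.
- No effect at all, two or more women below 90: about 19–46% at 150, 3–17% at 175, 0.4–5% at 200, at most 0.3% at 250. If only women who started at or above 90 count, the figure at 150 drops to about 5–7%.

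The results range from negligible to most trials as the assumed mean moves from 150 to 250.

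**The case against.** **The contradiction disappears if *However* is read as precedence.** This is a fair and probably natural reading. It would settle the overlap, so a reader who infers a flat contradiction goes further than the text. But precedence is only implied, and this reading leaves the empty row, the missing baseline condition and the word *statistically* untouched.

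**The empty row can be inferred from the hypothesis.** A fall of 30% or more without breaches can be read as an interaction with suppression maintained. That is reasonable, but the Interpretation paragraph does not say it. Nor is a large fall remote: Section 3 cites large decreases with EFV, although Section 6 calls the effect of the lower dose unclear.

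**Women should not start below 90 pg/mL.** Section 3 says the implant keeps ENG above that level, and the terms *breach* and *decrease* suggest a crossing from above. This weakens the baseline point, and at assumed means of 200 or more it matters little. Still, the rule does not require a crossing, and no eligibility criterion guarantees one.

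**A reader might infer that the trial may end with no valid conclusion.** The documents do not support this. The before/after ENG change, AUC, Cmax, Cmin, hormones, ultrasound and mucus findings can be reported in every row, and the study is a single-arm pilot meant to guide later work.

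**Conclusion.** The point holds as a defect in the decision rules. They are neither mutually exclusive nor exhaustive: one of four outcomes meets both, with precedence only hinted at, and one has no conclusion although it matches the plan's own expectation. These findings need only the plan's figures.

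The claim of statistical significance for two of 15 is unsupported unless the background breach rate is about 2.4% or less, a rate the plan does not give. The missing baseline condition means the rule can report a decrease where nothing changed.

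It would be tempting to attach one probability to a conflicting or missing conclusion. The plan gives no baseline mean or CV, and the simulated figures swing too widely with those assumptions for any single likelihood to be quoted. The consequence is a contradictory or absent pre-specified interpretation for some plausible results.

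**What to change.** Replace the two rules in Section 7c with one decision table, based on the within-woman Day 14/Day 1 ENG ratio (which matches the primary outcome) and reported with its confidence interval:

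1. Fall under 30%, fewer than two new breaches: no significant interaction.
2. Fall under 30%, two or more new breaches: the breach finding prevails, and no significant interaction may not be concluded.
3. Fall of 30% or more, fewer than two new breaches: pharmacokinetic interaction, with concentrations largely above the threshold.
4. Fall of 30% or more, two or more new breaches: interaction with potential for decreased contraceptive efficacy.

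Count as new breaches only women at or above 90 pg/mL at the Day 1 pre-dose baseline. Drop *statistically* from the breach rule and report the count with an exact confidence interval.

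The table should also state which visit or visits count for a breach, how the three pre-dose samples are combined, whether the 30% applies to the estimate or to a confidence limit, and what happens if the evaluable number is not 15. The sample-size sentence, written for historical controls, should be aligned with the within-woman comparison.

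Cost: a few lines of text and no new data, since the Day 1 pre-dose samples are already scheduled. It becomes slightly harder to declare no interaction.
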